7.3 Number of Patients to be Enrolled

The primary endpoint of this study is the proportion of subjects who achieve DAS28 (CRP) remission (DAS28 <2.6) after 52 weeks of adalimumab + high dose MTX. Based on data from another trial assessing the effectiveness of adalimumab in daily clinical practice, the following power calculation was done⁹⁾. With a significance level of 0.05 (two-sided) and a power of 0.90 (1-β), 350 subjects are required to detect an expected remission rate, i.e., the percentage of patients with the DAS28 score of <2.6 at week 52.

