13.1 Sample Size Calculation

The primary endpoint of this study is the proportion of subjects who achieve DAS28 (CRP) remission (DAS28 <2.6) after 52 weeks of adalimumab + high dose MTX. We calculated the target sample number for this survey on the basis of an expected remission

rate, i.e., the percentage of patients with a DAS28 score of <2.6, at week 52 during the treatment with adalimumab 40 mg and MTX at ≥ 12 mg/week.

Table 3 lists the percentages of patients with a DAS28 score of <2.6 at week 52 in a study conducted by Takeuchi et al.⁹⁾ in patients receiving adalimumab and MTX.

Table 3. Patients with a DAS 28 score of <2.6 at week 52 during the treatment with adalimumab and MTX

adalimumab + MTX dose (mg/week)	Percentage of patients with DAS28 <2.6 (Week 52)
8.5 ± 2.9	42.7% (61/143 patients)
≥ 12	61.7% (29/47 patients)

As Table 3 shows, 42.7% of patients receiving MTX at 8.5 ± 2.9 mg/week at the initiation of adalimumab treatment achieved a DAS 28 of <2.6 at week 52, and the corresponding percentage of patients receiving DAS at ≥ 12 mg/week at baseline was 61.7%. When 55% of patients receiving MTX at ≥ 12 mg/week at the initiation of adalimumab treatment are assumed to achieve a DAS 28 of <2.6 at week 52 (subtracting the standard error (7.10%) from the above mentioned percentage; $61.7 - 7.1 = 54.6\%$), the number of patients required to achieve a power ($1-\beta$) of 0.90 at an α level of 0.05 (two-tailed) would be 171 (one-sample test).

Since 32% of patients enrolled in the all-case survey of adalimumab in patients with rheumatoid arthritis dropped out during the 24-week survey period, we assumed that 50% of the participants in the survey would drop out during the 52-week survey period, and calculated that 342 patients should enroll in the survey. We thus set the target sample size at 350.

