4.2. Survey plan

(1) Survey subjects

Japanese RA patients who receive Humira meeting the following conditions.

- 1) Patients with the duration of RA within 2 years from the diagnosis at the start of Humira treatment
- 2) Patients receiving MTX for 3 months or longer at the start of Humira treatment
- 3) Patients receiving more than 12 mg/week of MTX at the start of Humira treatment
- 4) Patients with DAS28 (CRP) > 3.2 at the start of Humira treatment (4 weeks prior to treatment start - start date of treatment)

(2) Patients excluded from the survey

- 1) Patients who have received biological products

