4.3. Planned sample size

(1) Planned number of patients surveyed

350 patients

(2) Rationale for setting

The patient with Disease Activity Score 28 (hereafter, referred to as “DAS28”) below 2.6 at week 52 was estimated to be 55% (the expected observation was 55% and the estimated difference was 12.3% for the literature data 42.7%), and the number of patients required to detect at a 5% level of significance level (paired) and a 90% power was calculated to be 171 patients. As the number needed to treat to secure this number of patients, the dropout rate at week 52 in this survey was assumed to be 50% based on the dropout rate of approximately 32% at week 24 in the all-case surveillance with Humira, and the planned number of patients surveyed was calculated to be 350 patients.

5. Items to be evaluated in analysis and examining method

(1) Analysis items

1) Matters concerning patient composition

- 1) Number of patients with returned CRFs
- 2) Number of patients included in the safety analysis set
- 3) Number of patients included in the efficacy analysis set

- 2) Matters concerning safety
 - 1) List of incidences of ADRs/infections
 - 2) Factors considered to have an influence on safety
Incidence of ADRs by patient background factor, etc.
 - 3) AEs occurred during or after treatment
List of incidences of serious AEs, etc.
 - 3) Matters concerning efficacy
 - 1) DAS28 response, trend, percentage of remission, etc.
 - 2) CDAI response, trend, percentage of remission, etc.
 - 3) SDAI response, trend, percentage of remission, etc.
 - 4) Trends in HAQ, etc.
 - 5) Trends in EQ-5D, etc.
 - 6) Trends in mTSS/bone erosion score/joint space narrowing score and the percentage of patients without worsening of mTSS/bone erosion score/joint space narrowing score (change from the survey start < 0 and < 0.5), etc.
 - 7) Factors considered to have an influence on efficacy (list of efficacy by patient background factor, etc.)
- (2) Analysis methods
Appropriate methods including χ^2 test according to the scale and nature of the analysis data should be used.

6. Schedule of the analysis

Purpose of the analysis	Survey unit period and time frame for reexamination
The 11th Periodic Safety Report	December 31, 2012 - June 30, 2013
The 12th Periodic Safety Report	July 1, 2013 - December 31, 2013
The 13th Periodic Safety Report	January 1, 2014 - June 30, 2014
The 14th Periodic Safety Report	July 1, 2014 - December 31, 2014

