Prior to treatment start	Data included in the period between the date of initial Humira treatment -28 days and the date of initial Humira treatment and the closest data to the date of initial Humira treatment should be adopted.
At week 12	Data included in the period between the date of initial Humira treatment +56 days and the date of initial Humira treatment +112 days and the closest data to the date of initial Humira treatment +84 days should be adopted.
At week 24	Data included in the period between the date of initial Humira treatment +140 days and the date of initial Humira treatment +196 days and the closest data to the date of initial Humira treatment +168 days should be adopted.
At week 52	Data included in the period between the date of initial Humira treatment +336 days and the date of initial Humira treatment +392 days and the closest data to the date of initial Humira treatment +364 days should be adopted.
At week 76	Data included in the period between the date of initial Humira treatment +504 days and the date of initial Humira treatment +560 days and the closest data to the date of initial Humira treatment +532 days should be adopted.
At week 104	Data included in the period between the date of initial Humira treatment +700 days and the date of initial Humira treatment +756 days and the closest data to the date of initial Humira treatment +728 days should be adopted.
At final evaluation	The final data of the patient among the data included in the period between the date of initial Humira treatment +1 day and the final evaluation date should be adopted.

For data entered at each evaluation timing of mTSS, bone erosion score and joint space narrowing score when evaluating efficacy regarding administration of Humira, the acceptability of data by timing should be judged based on the acceptable range of the timing. The acceptable range of the timing is shown in the table below.

If there is more than one data within the acceptable range of the timing, the data on the closest date to the reference date should be adopted. If there is more than one data within the acceptable range of the timing with the equal number of days from the reference before and after the reference date respectively, the data before the reference date should be adopted.

Additionally, it should follow the following provision for the data included in the following acceptable range.

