“Table 6.2.3 Change of DAS28-4CRP Over Time”

Note: The patients included in the efficacy analysis set (DAS28-4CRP) should be handled as the analysis objects and tabulated by DAS28-4CRP category.

“Table 6.3.1 Change of CDAI Over Time”

Note: The patients included in the efficacy analysis set (CDAI) should be handled as the analysis objects and tabulated by CDAI category.

“Table 6.4.1 Change of SDAI Over Time”

Note: The patients included in the efficacy analysis set (SDAI) should be handled as the analysis objects and tabulated by SDAI category.

“Table 6.5.1 Change of HAQ-DI Over Time”

Note: The patients included in the efficacy analysis set (HAQ-DI) should be handled as the analysis objects and tabulated by HAQ-DI category.

The above figures and tables should be prepared only at the time of literature analysis.

“Table 6.2 DAS28-4CRP response, trend, percentage of remission”

Analysis object: Patients included in the efficacy analysis set (DAS28-4CRP)

Purpose of analysis: To indicate the number of patients and summary statistics of the score and response by evaluation time for the DAS28-4CRP and conduct a paired t test for the response from baseline. In addition, the number and the percentage of patients, number of patients with Low+Remission and Remission, point estimate and 95% CI of the percentage by DAS28-4ESR category by evaluation time should be indicated, and McNemer test should be performed for the percentage change from baseline.

The DAS28-4CRP category should follow “11. Data-layer separation.”

Note: The same form should also be prepared in literature analysis.

“Table 6.2.2 Summary of DAS28-4CRP by each Visit per Increase/decrease MTX Dose of up to Week 52 (literature analysis)”

Analysis object: Patients included in the efficacy analysis set (DAS28-4CRP)

Purpose of analysis: To indicate the number of patients by evaluation time, and the summary statistics of the scores and response for the DAS28-4CRP scores stratified by the groups based on the increase and decrease of MTX dose at week 52 and conduct a paired t test for the response from baseline.

The response should be compared between the groups by analysis of variance by evaluation time.

Note: It should be categorized by the following three categories based on the increase and decrease of the MTX dose from the start of Humira treatment to week 52: “ $2 \leq$,” “ $-2 < < 2$,” and “ < -2 .”

This form should be prepared only at the time of literature analysis.

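### The SAP never compares week-52 DAS28-CRP remission with the 42.7% used for sizing; its only test of that percentage is McNemar against a baseline that should be almost empty

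*SAP*

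**What the plan says.** Protocol 7.3 defines the endpoint: "The primary endpoint of this study is the proportion of subjects who achieve DAS28 (CRP) remission", meaning DAS28 below 2.6 after 52 weeks.

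Protocol 13.1 gives the sizing. Table 3 there lists a literature rate of "42.7% (61/143 patients") for adalimumab with MTX at 8.5 ± 2.9 mg/week. The text assumes 55% for this study and states that, at two-tailed 0.05 and power 0.90, the number required "would be 171 (one-sample test"). SAP 4.3 names the comparator: "the expected observation was 55% and the estimated difference was 12.3% for the literature data 42.7" per cent. It repeats the number but describes the test differently: "detect at a 5% level of significance level (paired) and a 90% power was calculated to be 171 patients".

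For the analysis, Table 6.2 (SAP 13.3) plans, at each evaluation time, DAS28-4CRP summary statistics with a paired t test on the score change, counts and percentages by category, and a point estimate and 95% CI for Remission and for Low+Remission. For the percentages it adds that a "McNemer test should be performed for the percentage change from baseline". It asks for the CI by DAS28-4ESR category, although the table concerns DAS28-4CRP.

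On baseline, SAP 4.2 admits "Patients with DAS28 (CRP) > 3.2 at the start of Humira treatment", measured in the four weeks up to the start date. SAP Section 12 takes the analysed baseline from a similar window: "the date of initial Humira treatment -28 days and the date of initial Humira treatment and the closest data" to the start.

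**The concern.** The powered comparison and the planned test answer different questions. The first asks whether the week-52 remission rate differs from 42.7%. The second asks whether more patients entered remission than left it, in a cohort selected so that practically nobody starts there. Rejecting that null says almost nothing about how good the week-52 rate is.

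Followed as written, the SAP would print one p-value for the primary percentage. That p-value would be extremely small even if remission were clearly worse than the reference. SAP 9.6 calls any p below 0.05 significant, and SAP 3.1 says the results feed reporting to authorities and reexamination materials. The 90% power would belong to an analysis that is never specified, and how the CI is read against 42.7% would be left open until the data are in.

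**Working it through.** **Inputs.** Reference p0 = 0.427 (Protocol 13.1, Table 3; SAP 4.3). Expected p1 = 0.55 and difference 0.123 (SAP 4.3). Two-sided 0.05, power 0.90, one-sample (Protocol 13.1). Evaluable n = 171.

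**Step 1: reproduce 171.** One-sample normal approximation:

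n = [1.960 × √(p0(1−p0)) + 1.2816 × √(p1(1−p1))]² / (p1−p0)²
= [1.960 × 0.4946 + 1.2816 × 0.4975]² / 0.123² = 170.7, so 171.

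With 50% dropout, 171/0.5 = 342, rounded up to 350. The plan's figure is therefore a one-sample test against a fixed 42.7%. The word (paired) in SAP 4.3 does not describe this calculation.

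**Step 2: look for that test in the SAP.** After SAP 4.3 the value 42.7% does not appear again. The tables using DAS28-4CRP are:
- 6.2: CI without a reference value; McNemar against baseline.
- 6.2.2, 6.2.4, 6.2.5: tests on scores.
- 6.2.6: remission at week 104.
- 6.2.7.1 to 6.2.7.4: remission at week 12 or 24.
- 1.4, 1.5 and the 6.8 series: EULAR response.

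SAP Section 5(2) adds only a general reference to appropriate methods, including χ². No table tests week-52 remission against 42.7%.

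**Step 3: what the sized comparison requires at n = 171.** Score test: z = (k/171 − 0.427)/√(0.427 × 0.573/171), with denominator 0.0378.

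| Remitters | Rate | Score p | Wilson 95% CI |
|---|---|---|---|
| 60 | 35.1% | 0.044 | 28.3% to 42.5% |
| 85 | 49.7% | 0.064 | 42.3% to 57.1% |
| 86 | 50.3% | 0.045 | 42.9% to 57.7% |

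The test favours the new rate from 86 upwards. Exact binomial power at 55% is 90.5% and actual two-sided size is 5.3%. The exact binomial test needs 87 (50.9%, p = 0.037), with power 87.7%.

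**Step 4: what McNemar requires.** Let b be baseline remitters who lose remission and c be new remitters. With b = 0, exact p = 2 × 0.5^c:
- c = 6 (3.5% of 171): p = 0.031. The uncorrected χ² already reaches p = 0.046 at c = 4 (2.3%).
- c = 60: p = 1.7e-18, although this rate is significantly below 42.7% by the score test.
- c = 73 (42.7%, the reference itself): p = 2e-22.
- If the true remission rate were only 10%, the chance of at least 6 remitters is 0.9996.

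**Step 5: sensitivity to a non-empty baseline.** Zero baseline remitters is an inference. Several readings can fall in the 28-day window, the exclusion criteria are in a separate document, and SAP Section 11 lists a baseline stratum below 2.6. If 5 patients were in remission at baseline and all lost it, 15 new remitters would suffice and 60 would give p = 4.9e-13. The conclusion does not change.

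**The case against.** The strongest reply is that this is a single-arm observational survey whose synopsis describes a mainly descriptive approach, and that Table 6.2 already gives the estimate and 95% CI that answer the objective. With 42.7% in SAP 4.3 and two-sided 5% in SAP 9.6, any reader can hold the CI against the reference. At 171 the Wald and Wilson limits clear 42.7% at 86 remitters and Clopper-Pearson at 87, so the CI method moves the verdict by at most one patient. McNemar is a template line repeated in Tables 6.1 to 6.5 and is nowhere called primary. Finally, 42.7% comes from a retrospective study at a lower MTX dose, so a p-value against it could itself mislead.

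Much of this stands. The CI limits the harm, McNemar is not labelled primary, and the 60/171 example sits at the boundary: 61 gives p = 0.063, and the Clopper-Pearson upper limit at 60 is 42.74%, just covering 42.7%. Protocol 13.1 also lists 42.7% without calling it the null; only SAP 4.3 does so explicitly.

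It does not remove the gap. Protocol 13.4 provides for inference at 0.05, the sample size is that of a powered test, and Protocol 13.0 says the SAP will set out all procedures in detail. No CI method is named, and at 86/171 Wilson excludes 42.7% (lower limit 42.9%) while Clopper-Pearson does not (42.6%). That choice should be fixed before the data are seen. If only description was intended, McNemar should not be printed on this endpoint either.

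**Conclusion.** The concern holds and should be fixed. The comparison behind the 171 patients is missing from the SAP. The only test of the primary percentage is significant from about 3.5% remission, against 50.3% for the sized comparison, so it cannot serve as evidence on the primary endpoint.

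The figures assume 171 evaluable patients and no baseline remitters, or 5 in the sensitivity case. They also treat 42.7% as fixed, as the sizing does, although it is an estimate: 61/143 has standard error 4.1 points and Wilson 95% CI 34.8% to 50.9%. The two wording errors are editorial and leave the sample size unchanged, but both sit in text that defines the primary analysis.

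**What to change.** - **Table 6.2:** name as the primary week-52 analysis a two-sided one-sample score test of DAS28-4CRP Remission against 0.427, with the Wilson 95% CI read against 42.7%. This matches the sizing formula, and test and CI agree at the upper cut-off of 86/171. If an exact test is preferred, say so and state that it needs 87/171 with 87.7% power.
- **Benchmark:** state that 42.7% is treated as a fixed value although it was estimated from 143 patients.
- **McNemar:** for DAS28-4CRP Remission and Low+Remission, label it descriptive or drop it, and do not cite it for the primary endpoint.
- **Wording:** in SAP 4.3 replace (paired) with two-sided, one-sample; in Table 6.2 replace the DAS28-4ESR category with the DAS28-4CRP category.

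The cost is a few lines of SAP text and one line of code. Reference, significance level and test type are already documented, so nothing is data-driven. The drawbacks are that the comparison can come out non-significant, that the score test's actual size is 5.3%, and that the result holds only against a fixed benchmark. If the sampling error of 61/143 were counted, a two-sample normal approximation (55% of 171 against 42.7% of 143) gives power of about 58%.

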“Table 6.2.4 Summary of DAS28-4CRP by each Visit per Baseline MTX Dose”

Analysis object: Patients included in the efficacy analysis set (DAS28-4CRP)

Purpose of analysis: To indicate the number of patients by evaluation time, and summary statistics of the score and response for the DAS28-4CRP score by the group of MTX dose at the start of Humira treatment.

In addition, paired t tests should be performed for the response from the start of treatment, and the results of intergroup comparison by analysis of variance should be calculated by evaluation time.

Note: The group separation should follow the concomitant MTX dose (mg/week) in the patient background in “11. Data-layer separation.”

This form should be prepared only at the time of literature analysis.

“Table 6.2.5 Summary of DAS28-4CRP by each Visit per Average Usage MTX Dose of up to week 52”

Analysis object: Patients included in the efficacy analysis set (DAS28-4CRP)

Purpose of analysis: To indicate the number of patients by evaluation time, and summary statistics of the score and response for the DAS28-4CRP score by two groups of the mean MTX dose at week 52: < 12.0 mg/week group or ≥ 12.0 mg/week group. In addition, paired t tests should be performed for the response from baseline, and the results of intergroup comparison by analysis of variance should be calculated by evaluation time.

Note: It should be categorized by the following two categories based on the increase and decrease of the mean MTX dose from the start of Humira treatment to week 52: “< 12.0” and “12.0 \leq .”

This form should be prepared only at the time of literature analysis.

“Table 6.2.6 Univariate logistic analysis event: DAS28-4CRP ≤ 2.6 at week 104”

Analysis object: Patients included in the efficacy analysis set (DAS28-4CRP)

Purpose of analysis: To conduct univariate logistic regression analysis with the number of patients meeting the week 104 DAS28-4CRP < 2.6 as the objective variable and each patient background factor as the explanatory variable, and to indicate the number of patients analyzed, number of patients who developed ADRs, incidence rate, odds ratio, CI and p values.

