Purpose of analysis: To indicate the number of patients by evaluation time and the summary statistics of the score and the response for the joint space narrowing score and conduct a paired t test for the response from baseline. Additionally, the number and percentage of the patients by evaluation time by the category of the joint space narrowing score should be shown. The category of the joint space narrowing score should follow “11. Data-layer separation.”

Note: None in particular.

“Table 6.11.2 Percentage of patients without a trend or worsening of the joint space narrowing score (evaluation time at week 104)”

Analysis object: Patients included in the efficacy analysis set (mTSS at week 104)

Purpose of analysis: To tabulate the patients included in the efficacy analysis set (mTSS at week 104) by using the same tabulation technique as Table 6.11.1.

Note: None in particular.

“Table 7.1 Summary of MTX at each Period”

Analysis object: patients included in the safety analysis set

Purpose of analysis: to calculate the summary statistics of the MTX dose at treatment start, the mean MTX dose between treatment start and week 52, the mean MTX dose between treatment start and week 12, and the mean MTX dose between week 12 and week 52.

Note: This form should be prepared only at the time of literature analysis.

“Table 7.1.1 Summary of MTX Over Time”

Analysis object: Patients included in the safety analysis set

Purpose of analysis: To illustrate the followings by timing by a cumulative bar chart: MTX dose at treatment start, MTX dose at week 12, MTX dose at week 24, MTX dose at week 52, MTX dose at week 76, and MTX dose at week 104. At treatment start, at weeks 12, 24, 52, 76 and 104 should be established by the categories indicated in “12. Handling of data on test/evaluation time.”

Note: This form should be prepared only at the time of literature analysis.

“Table 7.1.2 Demographic data and baseline score each MTX Dose of Baseline”

Analysis object: Patients included in the efficacy analysis set

Purpose of analysis: To calculate the number and percentage of patients by patient background factor at the start of treatment, or the stratified summary statistics of MTX dose at the start of Humira treatment.

The patient background factors should follow “11. Data-layer separation.”

Note:

[Complication: liver disorders (hepatitis)]: The denominator of the percentage should be the number of patients with “hepatitis.”

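### SAP Table 6.2.2: the three MTX-change classes leave a change of exactly -2 mg/week unassigned, while exactly +2 counts as an increase (minor)

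*SAP*

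**What the plan says.** Table 6.2.2 (SAP 13.3, Efficacy) reports DAS28-4CRP scores and response at each evaluation time, "stratified by the groups based on the increase and decrease of MTX dose at week 52". Within each group a paired t test is run on the response from baseline. Across groups, "The response should be compared between the groups by analysis of variance by evaluation time".

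The note to the table defines the groups. It announces three of them: "It should be categorized by the following three categories based on the increase and decrease of the MTX dose from the start of Humira treatment". The bounds are "from the start of Humira treatment to week 52: “ $2 \leq$,” “ $-2 < < 2$,” and “ < -2". The note adds that the table is produced only for the literature analysis.

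Neither the derivation rules in SAP 10.1 nor the category lists in SAP 11 give another definition of these classes or a rule for a value on a bound.

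**The concern.** The two bounds are treated differently. A change of +2 is included in the increase class, but a change of -2 is excluded from both the middle class and the reduction class. A set of classes meant to sort all patients by direction of MTX change should place each possible value in exactly one class, and this one does not.

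If the text is programmed as printed, patients at exactly -2 vanish from the counts, the summary statistics, the paired t tests and the analysis of variance. The reduction group then holds only reductions larger than 2 mg/week, while the increase group includes increases of exactly 2 mg/week, so the two are not mirror images. A programmer who notices the gap would have to choose a class without guidance, and two programmers could choose differently.

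**Working it through.** **Inputs.** Class bounds: note to Table 6.2.2. Starting-dose bounds of 12, 14 and 16 mg/week: SAP 10.1 (concomitant MTX) and SAP 11. Maximum MTX dose of 16 mg/week: Protocol 5.0. The documents print no figure for this point, so there is none to reproduce.

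**Step 1: the classes as printed.** Let d be the change in MTX dose (mg/week).

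- Increase: d ≥ 2
- Middle: -2 < d < 2
- Reduction: d < -2

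The middle and increase classes together cover every d > -2. The reduction class covers every d < -2. The one value left over is d = -2. No value is in two classes.

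**Step 2: the two bounds side by side.**

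| d | d ≥ 2 | -2 < d < 2 | d < -2 | Class |
|---|---|---|---|---|
| +2 | yes | no | no | increase |
| -2 | no | no | no | none |

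**Step 3: is the missing value a realistic one?** This step needs two assumptions: that d is the week-52 dose minus the starting dose, and that doses move in steps of 2 mg/week. The second is suggested by the 2 mg spacing of the starting-dose bounds but is stated nowhere.

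- One step down: 12 to 10, 14 to 12, 16 to 14. All give d = -2, no class.
- Two steps down: 12 to 8, 14 to 10, 16 to 12. All give d = -4, reduction.
- One step up, within the stated maximum of 16: 12 to 14, 14 to 16. Both give d = +2, increase.

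On this grid the increase class begins at the first step, the reduction class at the second, and the middle class holds only d = 0.

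**Step 4: repairs.**

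- Reduction as d ≤ -2, others unchanged: d = -2 goes to reduction. The classes cover every value without overlap.
- Middle as -2 ≤ d < 2, others unchanged: d = -2 goes to the middle. Again full cover without overlap.

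**Step 5: neighbouring class systems.** Table 6.2.5 splits at 12.0 with one side closed, so it has no gap. The starting-dose classes used in Table 6.2.4 cover all doses from 12 upward. The DAS28, CDAI and SDAI categories in SAP 11 are also exhaustive. The gap in Table 6.2.2 therefore looks like a slip and not a deliberate exclusion.

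**The case against.** **It may be a typographical or text-extraction artefact.** Inequality signs vary elsewhere in the SAP. Section 5 gives strict bounds for the mTSS change where section 11 gives `≤ 0` and `≤ 0.5`, and the background list for Table 6.9.4.1 prints the sign of the top MTX class the wrong way round. A lost sign cannot be ruled out, although the `≤` in the first class of the same note survived. What stands is that the sponsor should check the source file. If the bound is closed there, nothing needs to change.

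**The change variable is not clearly defined.** A reader might infer that every patient with a net reduction of 2 mg/week is left out. That holds only if the change is week-52 dose minus starting dose, and the SAP does not settle this. Table 7.1 names an average explicitly ("the mean MTX dose between treatment start and week 52"), but Table 6.2.5 writes "by two groups of the mean MTX dose at week 52" for a dose that its title and note describe over the period up to week 52. Tables 6.2.7.1 to 6.2.7.4 speak of mean usage in their titles and simply of a change in dose in their text. If an average enters the calculation, a value of exactly -2 could be rare. This objection limits the size of the problem but does not remove the gap.

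**The repair is not unique.** This is correct. Symmetry with `2 ≤` favours `≤ -2`, but only the sponsor knows which class was meant.

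**A wider reading is tempting.** Because the groups in Tables 6.2.2 and 6.2.5 rest on dosing up to week 52, a reader might infer that their between-group p-values are presented as effects of MTX dose and that the plan is at fault for it. The documents do not support that. Nothing in them calls these p-values dose effects, the Protocol's synopsis sets a mainly descriptive approach, and Protocol 13.4 calls the significance level nominal. Tables 6.2.7.1 to 6.2.7.4 already relate remission at week 12 or 24 to later MTX changes. Other tables, such as 6.2.6 and 6.9.5.1, also use drug factors recorded during treatment. How to word the interpretation is a separate matter and not an error in the classification rule.

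**Conclusion.** The rule is wrong as written, and the issue is minor. That exactly -2 mg/week has no class follows from the printed inequalities alone and needs no assumption beyond the text being as printed.

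How many patients are affected cannot be derived from the documents. SAP 9.4 shows MTX dose to one decimal, but that is a rule on displayed digits and does not say which changes occur. The statement that -2 is the smallest reduction, with the printed reduction class starting at -4, rests on both assumptions in Step 3 of the working.

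The consequence is confined to Table 6.2.2. Week-52 remission by DAS28-4CRP is reported in Table 6.2, which does not use these classes, so the primary endpoint is unaffected.

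**What to change.** In the note to Table 6.2.2, print the last class as `≤ -2`. This mirrors `2 ≤` and makes the three classes exhaustive and non-overlapping. If the sponsor intended -2 to count as no material change, print the middle class as `-2 ≤ < 2` instead and leave the last class as it is. Only one of the two changes should be made.

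The cost is one symbol and a rerun of Table 6.2.2. No new data are needed. The change concerns an analysis class only and implies nothing about how MTX is dosed.
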